7.5 SAFETY OVERSIGHT

Assuring participant safety is an essential component of MACH15. Each participating PI has primary responsibility for the safety of the individual participants enrolled at his/her clinical site, while the DSMB will have primary responsibility for monitoring the accumulating trial data for signs of adverse trends in the trial. The safety of the participant is always a major concern and, if warranted, the PI and/or central safety monitors can recommend discontinuation of the trial intervention for a particular participant.

7.5.1 SAFETY SUBCOMMITTEE

The Safety Subcommittee will review trial data related to the overall safety of trial participation, address IRB/EC issues (related to participant safety) that may arise, review clinical practice-related issues and oversee the clinical safety of all trial participants. The Safety Subcommittee is chaired by a Central Monitor (CM). The CM is a masked physician and will be responsible for the review of the SAEs that might meet the requirement for DSMB and NIH/NIAAA reporting.

The Safety Subcommittee will meet regularly with the aim to review any safety issues related to screening and participation in the trial. In addition, this committee will discuss adverse event reports, ensure consistency in SAE/MACH15 AE coding and reporting, and review any potential trends. The Safety Subcommittee provides early monitoring of adverse events and ensures standardization of clinical practice and safety issues across all clinical sites.

7.5.2 DATA AND SAFETY MONITORING BOARD (DSMB)

The DSMB appointed to monitor the safety of the MACH15 Trial is described in *Chapter 11: Trial Organization, Section 11.2.4* and the review and the evaluation of safety data is described in *Chapter 8: Statistical Considerations, Section 8.5*.

8.1 STATISTICAL ANALYSIS PLAN

The major statistical approaches and analyses that will be performed during the MACH15 Trial are described in this chapter.

8.1.1 PRIMARY AND SECONDARY OUTCOME ANALYSES

The primary analysis will assess the significance of any difference observed in the distribution of time from randomization until occurrence of the primary endpoint, an expanded cardiovascular disease (CVD) endpoint which includes death from any cause, using censored survival data analysis methods for clustered data. A detailed definition of the endpoint is given in *Chapter 3: Trial Design and Clinical Outcome Measures*. Kaplan-Meier estimates of survival will be obtained for participants randomized to each arm, taking into account household clustering,¹ and the log-rank test for clustered data,²⁻⁵ stratified by clinical site, and will be used to assess the statistical significance of any differences observed. The primary comparisons of intervention groups will be performed according to the “intention to treat” principle: all randomized participants will be grouped according to their intervention assigned at randomization. Hazard ratios and 95% confidence intervals will be calculated using Cox regression model for clustered data,^{6,7} adjusted for clinical site by a set of indicator variables. Estimates for the proportion of participants who remain event-free at pre-specified time points, and the associated confidence intervals, will be calculated similarly. Log-log plots of survival will be used to examine the assumption of proportional hazards, and effect modification by time since randomization will be assessed through the introduction of indicator variables for each 6-monthly or annual time period. If the proportional hazards assumption is not justified, in secondary analysis, we will report time-specific effect estimates and consider the use of accelerated failure time models which may provide a more parsimonious fit to the data. Should best practices for statistical analysis of trials with designs similar to MACH15 develop during the course this trial, the analysis plan will be revised accordingly. The analysis of the secondary endpoint, incidence of diabetes, will be conducted as described above.

There are numerous risk factors for CVD and diabetes, and these will be measured at baseline and at subsequent visits, including age, body mass index, hemoglobin, blood pressure, gender, race/ethnicity, healthy lifestyle, and other co-morbidities. Although randomization ensures that, on average, treatment groups will be balanced with respect to all of these factors, this may not be true in the given trial. Thus, we will assess the success of randomization by first comparing the baseline characteristics of participants in the treatment groups, and then re-assess treatment effects in secondary analysis after adjusting for the risk factors associated with the strongest imbalances. To adjust as finely as possible for confounding by measured risk factors, an additional secondary analysis will be conducted that adjusts for all measured risk factors.

Non-adherence to the assigned treatment is another potential challenge to power an unbiased treatment effect estimation that we will address in secondary sensitivity analysis by conducting *per protocol* and *as treated* analyses,⁸ by using instrumental variables methods,^{9,10} by potential outcomes

approaches,¹¹ by comparing the compliance estimates and by computing log rank tests weighted by time-varying probability of adherence.¹² *Per protocol* analysis excludes non-compliant participants from their respective arms. *As treated* analysis ignores treatment assignment but, rather, analyzes participants according to the amount of alcohol intake reported, regardless of what was assigned. The “contamination-adjusted intention-to-treat” uses instrumental variable analysis to address non-adherence in a two-stage approach. The potential outcomes approach is an estimation procedure for the intention-to-treat effect that maintains randomization-based properties under more plausible, non-ignorable noncompliance and non-ignorable missing-outcome conditions. The log rank tests weighted by time-varying probability of adherence involves modeling the probability of non-adherence given available covariate data, and then uses the inverse of these estimated probabilities, suitably stabilized, to reweight the log rank test statistic to mimic the study population that would have been observed, had there been no non-adherence

To assess adherence during the first year of the trial, the change in high density lipoprotein cholesterol (HDL-C) will be compared over an approximate 6-month period between the two groups. Based on a two sample t-test, the mean change in the intervention arm to the mean change in the abstention arm will be compared. Since this analysis is based upon individual level change scores, there is no need to control for clinical site or other time-invariant covariates.

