3.4.2. TERTIARY HYPOTHESES

- Among participants free of pre-diabetes or diabetes at enrollment, does one standard serving (~15 g) of alcohol daily reduce the rate of pre-diabetes compared to abstention from alcohol?

This hypothesis will be tested using a tertiary outcome of progression among normoglycemic individuals to ADA-defined prediabetes.

- Does one standard serving (~15 g) of alcohol consumption daily reduce the rate of hard CVD or cardiovascular mortality compared to abstention from alcohol?

This hypothesis will be tested using a tertiary outcome of time from baseline to a composite endpoint comprised of the first occurrence during follow-up of a non-fatal myocardial infarction, non-fatal ischemic stroke, or cardiovascular death.

- Does one standard serving (~15 g) of alcohol consumption daily reduce the rate of individual cardiovascular events or mortality compared to abstention from alcohol?

This hypothesis will be tested using tertiary outcomes of time from baseline to individual endpoints comprised of the first occurrences during follow-up of myocardial infarction, ischemic stroke, hospitalization for angina, coronary/carotid revascularization, all-cause mortality, and cardiovascular mortality.

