3.5.1 TRIAL OUTCOMES

The primary, secondary, and tertiary outcomes are as follows:

Primary:

Time from baseline to a composite endpoint comprised of the first occurrence of a non-fatal myocardial infarction, non-fatal ischemic stroke, hospitalization for angina, coronary/carotid revascularization, or all-cause mortality.

Secondary:

1. Time from baseline to a composite endpoint comprised of the first occurrence of a non-fatal myocardial infarction, non-fatal ischemic stroke, hospitalization for angina, coronary/carotid revascularization, or cardiovascular death.
2. Progression among normoglycemic and pre-diabetes individuals to American Diabetes Association (ADA)-defined diabetes.¹

Tertiary:

1. Time from baseline to a composite endpoint comprised of the first occurrence of a non-fatal myocardial infarction, non-fatal ischemic stroke, or cardiovascular death.
2. Time from baseline to the first occurrence of each of the components of primary outcome (5 outcomes).
3. Time from baseline to cardiovascular death.
4. Progression among normoglycemic individuals to ADA-defined prediabetes.¹

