8.1.3 INTERIM ANALYSIS

At the discretion of the Data and Safety Monitoring Board (DSMB), interim analyses will be performed periodically. Each meeting will include an administrative review to assess accrual, retention and the progress of the trial. In addition, there will be a review of efficacy, safety, and the occurrence of any adverse effects. For early stopping for efficacy, it will be suggested that the trial be stopped if the p-value for the log rank test for the primary endpoint and secondary endpoint are both < 0.001, following the Haybittle-Peto rule,^{13,14} and if, in addition, the results for other endpoints, including fatal and non-fatal myocardial infarction (MI), fatal CVD, hospitalized angina, revascularization, ischemic stroke and all-cause mortality are consistent with the results for incident CVD and diabetes. Futility analysis will be done once per year for the duration of the trial up to the sixth year, where at each time, given the observed data up to that point, the probability of observing an effect of the hypothesized value or anything more extreme would be less than 5% for both the pre-specified primary and secondary

endpoint. Safety and adverse events will be carefully monitored, including total and clinical site-specific cancer, hospitalizations, motor vehicle collisions, falls, fall-related fractures, alcohol misuse, atrial fibrillation, hemorrhagic stroke and increase in liver function tests to >2X ULN, and unmasking and stopping for safety will be considered should rates in the intervention arm appear unacceptably elevated compared to the abstention arm, accounting for multiple comparisons and adequate follow-up.

An interim analysis of HDL-C is described in Table 8.4 below. Results of this analysis will also be brought to the DSMB, with a discussion of stopping if no difference in levels between study arms is observed.

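### Kaplan-Meier is carried over from the primary endpoint to incident diabetes, where death is a competing event that the plan does not address, so diabetes probabilities may be modestly overstated

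*Combined protocol and SAP*

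**What the plan says.** Section 8.1.1 describes the primary outcome as "an expanded cardiovascular disease (CVD) endpoint which includes death from any cause, using censored survival data analysis methods for clustered data". The tools are Kaplan-Meier curves ("Kaplan-Meier estimates of survival will be obtained for participants randomized to each arm"), a log-rank test for clustered data stratified by site, and Cox regression for clustered data. It adds: "Estimates for the proportion of participants who remain event-free at pre-specified time points, and the associated confidence intervals, will be calculated similarly". On diabetes it has one sentence: "The analysis of the secondary endpoint, incidence of diabetes, will be conducted as described above".

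Section 3.5.1 lists a further secondary outcome, the composite that ends in "hospitalization for angina, coronary/carotid revascularization, or cardiovascular death", and several tertiary outcomes. Section 8.1.1 names no estimator for any of these. Chapter 8 mentions neither competing risks nor cumulative incidence.

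On the component outcomes, section 3.5.1 has "first occurrence of each of the components of primary outcome (5 outcomes", and the primary outcome there contains non-fatal MI and non-fatal ischemic stroke. Section 3.4.2 instead has "first occurrences during follow-up of myocardial infarction, ischemic stroke, hospitalization for angina" and so on, with no non-fatal limit.

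**The concern.** Kaplan-Meier treats a censored person as someone who could still have the event later. That holds for loss to follow-up under the usual assumptions. It cannot hold for a person who has died without diabetes. With deaths censored, one minus Kaplan-Meier estimates the diabetes risk that would be seen if nobody died, which is not the share of participants who develop diabetes. Nor is the Kaplan-Meier curve itself the share who remain event-free.

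Death is not negligible in this population. Participants are at least 50 years old, age 75 or over alone meets the risk criterion in section 4.2, and follow-up runs from 4.5 to 7.5 years. What is at stake is the absolute risk of diabetes in each arm, and any difference a reader takes between them, in a trial meant to inform drinking guidelines.

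The component outcomes raise a separate matter of definition: two analysts could count different MI and stroke events from the same data.

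**Working it through.** **Inputs from the documents.** Diabetes rate 0.017 per person-year in the abstention arm; 5,850 participants free of diabetes (2,925 per arm); 1% annual loss; 10% non-adherence; RR 0.75 (section 8.2). Mean follow-up 6 years, range 4.5 to 7.5 (section 11.4).

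**Assumed.** Constant hazards, and a death rate d before diabetes of 0.5% to 2.6% per year. The documents give no death rate. The upper end is the plan's rate for the whole primary composite, of which death is one part. It is an approximate ceiling only, because that rate counts first events and so omits deaths after a non-fatal event.

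**The plan's own figures first.** The cited cohort's 8.2% over 5 years gives −ln(1 − 0.082)/5 = 0.0171 per year, matching the stated 0.017. For Table 8.2, the effective HR is 1 − 0.9 × 0.25 = 0.775. With follow-up uniform on 4.5 to 7.5 years and household clustering ignored, 491 events are expected. Power = Φ(√491/2 × |ln 0.775| − 1.96) = Φ(0.864) = 80.6%, against 80% stated. All nine cells reproduce within one point.

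**Abstention arm at 6 years.** With h = 0.017:

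- One minus Kaplan-Meier = 1 − exp(−h × 6) = 1 − exp(−0.102) = 9.70%.
- Cumulative incidence = h/(h + d) × [1 − exp(−(h + d) × 6)]. At d = 0.02 this is 0.017/0.037 × [1 − exp(−0.222)] = 9.15%.

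**Difference between arms.** The alcohol-arm rate is 0.017 × 0.775 = 0.013175. One minus Kaplan-Meier is 1 − exp(−0.07905) = 7.60%, so the Kaplan-Meier difference is 9.70 − 7.60 = 2.10 points. The cumulative-incidence differences use the formula above in each arm, with the same d.

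| Assumed death rate per year | Cumulative incidence, abstention | Kaplan-Meier excess, points | Relative excess | Risk difference by cumulative incidence (Kaplan-Meier: 2.10) |
|---|---|---|---|---|
| 0.5% | 9.56% | 0.14 | 1.5% | 2.07 |
| 1.0% | 9.42% | 0.28 | 3.0% | 2.04 |
| 2.0% | 9.15% | 0.55 | 6.0% | 1.98 |
| 2.6% | 8.99% | 0.71 | 7.9% | 1.95 |

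At 7.5 years one minus Kaplan-Meier is 11.97%, and the excess is 0.22 to 1.07 points over the same range.

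**If mortality differed by arm.** With alcohol-arm mortality at 0.838 of control (illustrative only), the cumulative-incidence differences become 2.05, 2.00, 1.91 and 1.86 points.

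**The cardiovascular-death composite, if Kaplan-Meier were used there.** Suppose 0.2% to 1.3% per year of the 2.6% is non-cardiovascular death as the first event (assumed). The 6-year excess is then 0.08 to 0.28 points.

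**Component outcomes.** Section 3.5.1 has five components, with cardiovascular death as a separate tertiary outcome, making six. Section 3.4.2 also lists six endpoints. The counts agree; only the non-fatal limit on MI and ischemic stroke differs. Section 3.5.2 defines fatal and non-fatal forms of both, so it does not settle the matter.

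**The case against.** The strongest reply is that nothing confirmatory changes. The primary endpoint contains every death, so Kaplan-Meier is right for it. For diabetes, the log-rank test and the Cox hazard ratio with deaths censored remain valid comparisons of the cause-specific hazard. Section 8.1.1 promises hazard ratios and event-free proportions, not risk differences. The plan also does not state that deaths before diabetes are censored. All of this stands, and it limits the point to descriptive probabilities. But censoring is the natural reading when censored-data methods are applied to an endpoint without death, and the proportions are a stated deliverable.

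A reader might infer more than the documents support:

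- *That Kaplan-Meier is specified for the cardiovascular-death composite and the tertiary outcomes.* Section 8.1.1 extends its method to diabetes only. For the rest there is a gap, not a wrong specification.
- *That fatal MI and stroke drop out of the component outcomes.* This follows only from section 3.5.1; section 3.4.2 reads the other way. Fatal cases still count in the primary composite and in all-cause mortality. Section 8.1.3, "including fatal and non-fatal myocardial infarction (MI", is a consistency list for early stopping, so it is weak evidence for either reading.
- *That the plan expects alcohol to lower mortality, so the bias must differ by arm.* The figure of about 0.83 to 0.84 in section 1.2.2 is an observational association. Section 1.3.1 asserts equipoise, and section 8.2 assumes no separate mortality effect.
- *That the overstatement could be much larger.* A death rate of 3% per year, for example, would exceed the 2.6% the plan assumes for the whole composite.

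**Conclusion.** The point holds for diabetes, at modest size. If deaths are censored, the planned event-free proportions imply a 6-year diabetes risk 0.14 to 0.71 points too high (about 1.5% to 8% relative). The arm difference is 2.10 points rather than 2.07 to 1.95 with equal mortality. This rests on constant hazards, the plan's 1.7% per year, an effective HR of 0.775 for the difference, and the assumed death rates. For the cardiovascular-death composite and the tertiary outcomes that omit all-cause death, the defect is that no method is named. The disagreement between sections 3.5.1 and 3.4.2 is real and independent of the estimator. None of this touches the primary analysis or the diabetes hypothesis test.

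**What to change.** In section 8.1.1:

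1. For diabetes, report event probabilities by Aalen-Johansen cumulative incidence with death as a competing event, by arm, with intervals robust to household clustering. Show the probability of death without diabetes alongside.
2. Keep the log-rank test and Cox model, and label them as cause-specific comparisons with deaths censored.
3. Name the same estimator for the cardiovascular-death composite and for each tertiary outcome that omits all-cause death.

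In sections 3.4.2 and 3.5.1, state once whether the component MI and ischemic stroke outcomes include fatal cases, and use that definition throughout.

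The cost is a few sentences and standard software. Deaths are already collected as a trial outcome, so no new data and no change in sample size are needed. Section 8.1.1 already provides for revising the analysis plan; the change should be made before any comparison by arm is seen.

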4.2 PARTICIPANT INCLUSION CRITERIA

To be eligible for the MACH15 Trial an individual must meet all of the following criteria:

1. Age ≥ 50 years at screening
2. Postmenopausal, defined as 12 consecutive months without menstruation
3. Not alcohol naïve, defined by having consumed at least one drink of alcohol in the past five years
4. High risk for the occurrence of a new cardiovascular disease event, defined as having any one of the following:
 - a) American Heart Association (AHA)/American College of Cardiology (ACC) Risk Score $\geq 15\%$ within the past 24 months (among those without clinical or subclinical cardiovascular disease [CVD])
 - b) Clinical CVD (more than 6 months prior to randomization), defined by:
 - 1) Previous myocardial infarction (MI), percutaneous coronary intervention (PCI), coronary artery bypass grafting (CABG), carotid endarterectomy (CE), carotid stenting;
 - 2) Peripheral artery disease (PAD) with revascularization;

- 3) Acute coronary syndrome with or without resting electrocardiogram (ECG) change, ECG changes on a graded exercise test (GXT), or positive cardiac imaging study;
- 4) Prior stroke documented on brain imaging or with a persistent deficit.
- c) Subclinical CVD, confirmed in available medical records:
 - 1) At least a 50% diameter stenosis of a coronary, carotid, or lower extremity artery;
 - 2) Coronary artery calcium score ≥ 400 Agatston units;
 - 3) Ankle brachial index (ABI) ≤ 0.90 ;
 - 4) Left ventricular hypertrophy (LVH) by ECG (based on computer reading), echocardiogram report, or other cardiac imaging procedure report;
 - 5) Abdominal aortic aneurysm (AAA) ≥ 5 cm with or without repair.
- d) Age ≥ 75 years

Note that eligible individuals residing in the same household can participate if they agree to be randomized as a unit to the same intervention at the same randomization time.

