8.2 SAMPLE SIZE CALCULATIONS

Sample size calculations involved extensive explorations over a range of primary endpoint definitions and baseline rates, baseline adherence rates and improvements to these due to household network effects, proportions of households with 1, 2 and 3 eligible members, intra-household correlation coefficients, and minimum expected effect sizes.

We originally assumed that our trial will be individually randomized trial, and that the primary combined expanded CVD incidence endpoint in the abstention arm will have a rate of 0.026/person-year, modestly higher than the 2.2% annual rate observed in SPRINT,¹⁵ increased slightly because, unlike SPRINT, we are including diabetic individuals and total mortality as an outcome and excluding CHF alone. Participants will enroll during the first 3 years and then will be followed for an average of 6 years. We have assumed that there will be 1% annual loss to follow-up (LTF) in both groups, and 10% non-adherence at any point in time over follow-up for participants who are the sole person in their household to be randomized, leading, for these participants, to an effective hazard ratio of 0.838 under an assumed true hazard ratio of 0.82 as in Ronksley, et al.¹⁶ Under these assumptions, to provide a minimum of 80% power at a two-sided 0.05 significance level for detecting a 18% relative decrease in the intervention group endpoint rate, for an individually randomized trial design with one participant per household, we will need 3,900 participants per arm,¹⁷ for a total of 7,800.

Although we conservatively powered the trial for an expected relative risk (RR) of 0.82, there is substantial evidence suggesting that for CVD, an RR of 0.75 is likely to be observed. If so, we will have adequate power for baseline rates as low as approximately 0.0125/person-year, significantly lower than the observed rate in MESA.

[figure not shown]
TABLE 8.1: POWER FOR CARDIOVASCULAR DISEASE ANNUAL EVENT RATES

Annual Event Rate	Relative Risk		
	RR=0.82	RR=0.80	RR=0.75
1.4%	55%	65%	84%
1.8%	65%	75%	92%
2.2%	74%	83%	96%
2.6%	80%	88%	98%
3.0%	85%	92%	99%
3.4%	89%	94%	99%

Figure 8.1 presents power for different values of relative risks (0.80, 0.82 and 0.84) as a function of a range of plausible annual events rates (from 0.014/year to 0.035/year).

FIGURE 8.1: POWER FOR PRIMARY ENDPOINT

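### The primary test and hazard ratio in 8.1.1 use no prognostic baseline factor: a valid analysis that leaves roughly 1 to 4 points of power unused

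*Combined protocol and SAP*

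**What the plan says.** Section 8.1.1 tests the primary endpoint with a log-rank test for clustered data, "stratified by clinical site, and will be used to assess the statistical significance of any differences observed". The hazard ratio comes from a Cox model for clustered data, "adjusted for clinical site by a set of indicator variables". Household membership is handled in both, as a matter of variance. No prognostic covariate is in either.

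The same section plans two covariate-adjusted analyses, both labelled secondary. One adjusts for the factors found to be most imbalanced between arms, the other for every measured risk factor. The diabetes endpoint is to be analysed in the same way as the primary endpoint.

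Eligibility in 4.2 mixes several kinds of participant: "High risk for the occurrence of a new cardiovascular disease event, defined as having any one of the following", the options being a risk score of at least 15%, clinical CVD, subclinical CVD, or age 75 and over. The candidate covariates are collected at screening or baseline:
- age: 6.1.1.5
- medical history and comorbidities: 6.1.1.4
- smoking: 6.1.1.3
- glucose or HbA1c: Table 6.1, footnote 7
- gender: listed in 8.1.1 among the risk factors measured at baseline

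The documents give no reason for leaving these out of the primary analysis. Section 8.4 argues only against extra strata at randomization.

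**The concern.** The endpoint combines cardiovascular events with death from any cause, in people from age 50 upward, with and without prior events and with and without diabetes. Their risk will differ widely for reasons recorded at entry. In a time-to-event comparison, adjusting for strong baseline predictors gives a more powerful test from the same participants and events. Doing so only in secondary analyses leaves the primary p-value unchanged.

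The sizing has no reserve. The trial is planned "to provide a minimum of 80% power at a two-sided 0.05 significance level", and at a relative risk of 0.82 Table 8.1 already falls to 74% if the event rate is 2.2% a year instead of 2.6%. Even a few points of power would be useful.

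**Working it through.** **Inputs from 8.2 and 11.4.** The abstention arm "will have a rate of 0.026/person-year"; non-adherence leads "to an effective hazard ratio of 0.838 under an assumed true hazard ratio of 0.82"; "there will be 1% annual loss to follow-up (LTF) in both groups"; "we will need 3,900 participants per arm". Follow-up runs from 4.5 to 7.5 years, taken here as uniform. Household clustering (ICC 0.005) and site strata are left out of the integration below.

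**Step 1: reproduce the plan.** The effective hazard ratio is 1 − 0.9 × 0.18 = 0.838. With event rate λ and loss rate μ = 0.01,

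P(event) = λ/(λ+μ) × [1 − (e^(−4.5(λ+μ)) − e^(−7.5(λ+μ))) / (3(λ+μ))].

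- Abstention, λ = 0.026: 0.1400 × 3,900 = 546 events.
- Alcohol, λ = 0.026 × 0.838 = 0.02179: 0.1188 × 3,900 = 463 events.
- Total 1,009. Schoenfeld power = Φ(√(1,009/4) × |ln 0.838| − 1.96) = Φ(2.808 − 1.96) = 80.2%.
- Required events are 1,006 (Schoenfeld) or 1,011 (Freedman), so N is about 7,774 or 7,812 against the stated 7,800.
- The RR 0.82 column of Table 8.1 comes out at 55.3, 65.6, 73.8, 80.2, 85.1 and 88.8%, against the printed 55, 65, 74, 80, 85 and 89%.

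The plan's figures hold for its unadjusted test.

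**Step 2: add baseline prognosis.** The documents do not say how strongly the baseline factors predict the endpoint, so this is an assumption shown as a range. Let a normally distributed prognostic index with a given SD multiply the hazard. Set the baseline hazard so that the abstention rate stays at 0.026, and hold the unadjusted hazard ratio at 0.838. Numerical integration gives the expected Z of the unadjusted log-rank test (Z0) and of the test adjusted for the index (Z1). Power = Φ(Z − 1.96), information ratio = (Z1/Z0)², and equivalent N = 7,800 / information ratio.

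| Index SD | c-index | Z0 | Z1 | Information ratio | Adjusted power | Equivalent N |
|---|---|---|---|---|---|---|
| 0.4 | 0.61 | 2.802 | 2.835 | 1.024 | 80.9% | 7,616 |
| 0.5 | 0.63 | 2.801 | 2.856 | 1.039 | 81.5% | 7,505 |
| 0.6 | 0.66 | 2.801 | 2.883 | 1.059 | 82.2% | 7,365 |
| 0.8 | 0.70 | 2.800 | 2.957 | 1.116 | 84.1% | 6,992 |
| 1.0 | 0.75 | 2.799 | 3.064 | 1.199 | 86.5% | 6,507 |

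Unadjusted power is 80.0% in the first four rows and 79.9% in the last. At SD 0.8 the adjusted hazard ratio is 0.830 against 0.838 unadjusted.

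**Step 3: checks by simulation.**
- With 4,000 simulated trials of 7,800 at each of SD 0.5, 0.8 and 1.0, and the conditional hazard ratio set to 0.838, unadjusted power was 77.8, 75.6 and 73.0%. Adjusted power was 79.6, 80.2 and 80.1%. Integration under the same condition gives 78.5, 75.7 and 72.7% unadjusted and about 80% adjusted.
- A separate simulation (600 trials per scenario) used four explicit covariates: prior CVD (50%, assumed), age, diabetes (25%, from 8.2) and smoking (12%, assumed). For c-indices of about 0.62, 0.66 and 0.70 the information ratios were 1.021, 1.061 and 1.096, giving power of 80.8, 82.3 and 83.5%.
- In a similar simulation, adding 16 site strata left the information ratios almost unchanged.

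**The case against.** A site-stratified, cluster-adjusted log-rank test is valid, the sample size was set for that kind of test, and an unadjusted primary analysis with adjusted secondary ones is a common preference. That stands, and nothing in the plan is in error here.

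The gain is also small next to the planning uncertainty. At RR 0.82, Table 8.1 runs from 55% to 89% over event rates of 1.4% to 3.4%. Entry criteria that select people at above-average risk may narrow the spread of prognosis and push the gain toward one point. That stands too.

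Section 8.1.1 already promises an analysis adjusted for all measured risk factors, and allows revision as best practice develops. This softens the point without answering it. A secondary analysis does not supply the primary p-value, and a list chosen by observed imbalance is not a pre-specified prognostic list.

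Three stronger readings are tempting and are not supported:
- A reader might infer that the site-only hazard ratio is biased toward 1. It is not. It averages over the baseline factors, whereas the adjusted Cox hazard ratio is conditional on them. They are different quantities, and the gap is slight (0.838 against 0.830 at a c-index of 0.70).
- A reader might infer that the trial falls short of 80%. If 0.838 were the conditional hazard ratio, the planned test would have 79.1% to 75.7% power for SD 0.4 to 0.8. But 8.2 does not say that 0.82 is conditional on these covariates, and its figures reproduce when 0.838 is what the unadjusted test sees.
- A reader might call the gain free. It needs no extra participants or data, but it changes the target of the Cox estimate and affects other sections of the plan.

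**Conclusion.** The point holds as a missed efficiency in a valid analysis. Adjusting the primary test for prognostic factors already collected would raise power from 80% to roughly 81-84%. In information terms that is worth about 2% to 12%, equivalent to needing about 180 to 810 fewer participants for the same power (7,800 − 7,616 = 184; 7,800 − 6,992 = 808).

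The size rests on an assumed c-index of about 0.61 to 0.70, which the documents neither give nor rule out, with the low end plausible in this population. The direction does not depend on the exact value, provided that the factors predict the endpoint. The change is worthwhile because it costs little, and it keeps its value only if made before unblinded outcome data are seen.

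**What to change.** In 8.1.1, pre-specify before any unblinded outcome data are seen that the primary test and hazard ratio adjust for a short fixed list: age as a continuous term, sex, prior clinical CVD, diabetes status and current smoking. Stratify by site and use household-robust variance. Either a Cox model or a covariate-adjusted log-rank test will serve, provided that the latter also allows for household clustering. Report the site-only log-rank test and hazard ratio beside the adjusted results.

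Four details need settling at the same time:
- **Diabetes status.** Define it from what is recorded at screening or baseline before randomization. Under 6.3.5 the baseline visit is normally the randomization visit, and a raised value is confirmed by a later draw, so the confirmation may come after assignment.
- **Diabetes endpoint.** Drop baseline diabetes from its list. That population is free of diabetes at entry, so the covariate would be constant.
- **Interim rule.** Section 8.1.3 sets its threshold on the log-rank p-value for both endpoints. Align it with the adjusted test so that the interim and final analyses match.
- **Missing values.** State in advance how a missing covariate is handled.

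The cost is wording in 8.1.1 and 8.1.3, with no new data and no change in sample size. The downside is that an adjusted Cox hazard ratio is conditional on the listed covariates, which is why the site-only figure should stay in view.
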